## 21. COSTS TO SUBJECTS

- *Describe any foreseeable costs that subjects may incur through participation in the research*
- *Indicate whether research procedures will be billed to insurance or paid for by the research study.*

This research study is funded by the National Institutes for Health (NIH). All study related devices will be provided to participants at no cost. Participant insurance will not be billed.

This study uses text messaging to deliver notifications, reminders, and study questionnaires. Standard message and data rates from the participant's wireless carrier may apply to the study participant. Study participants will not be compensated for any costs related to data usage or sending or receiving text messages by the study or by members of the study team.

## 22. PAYMENT TO SUBJECTS

- *Describe the amount of payment to subjects, in what form payment will be received and the timing of the payments.*

There is no payment to subjects for participation in this research, however participants will be allowed to keep their Fitbit device if they –are randomized to the intervention phase.

## 23. CONSENT PROCESS

*If obtaining consent for this study, describe:*

- *Who will be obtaining consent*
- *Where consent will be obtained*
- *Any waiting period available between informing the prospective participant and obtaining consent*
- *Steps that will be taken to assure the participants' understanding*
- *Any tools that will be utilized during the consent process*
- *Information about how the consent will be documented in writing. If using a standard consent form, indicate such.*
- *Procedures for maintaining informed consent.*

Each subject will receive written explanations of the purposes, procedures, and risks of this study in language appropriate for the individual's level of understanding. All questions will be answered via email or phone, and if all inclusion criteria are met, and the subject volunteers to participate, digital written informed consent will be obtained.

Written, electronic consent (e-consent) will be obtained via REDCap, a web-based platform capable of recording electronic signature. The e-consent document will contain all of the elements of informed consent required by applicable federal regulation for the protection of human subjects and elements of authorization required by the HIPAA Privacy Rule, and will begin with a concise and focused presentation of the key information that is most likely to assist participants in understanding the reasons why he/she might or might not want to participate in the research.

Because consent will be obtained remotely, the electronic platform will be designed such that the consent form is easy to navigate. The system will also incorporate electronic strategies to encourage participants to access all of the consent material before documenting his/her consent.

We will also employ interactive electronic-based technology such as a comprehensive knowledge check at the end of the consent process. Participants may contact a member of the research team with questions about the research. Both the research phone and email inbox will be monitored daily by consenting coordinators.

PDF copies of signed consent forms will be electronically stored in a HIPAA-secured, Northwell approved storage drive with protected access to only the PI and research personnel listed on the study protocol.

*In the state of NY, any participants under the age of 18 are considered children. If your study involves children, additional information should be provided to describe:*

- *How parental permission will be obtained*
- *From how many parents will parental permission be obtained*
- *Whether permission will be obtained from individuals other than parents, and if so, who will be allowed to provide permission. The process used to determine these individual's authority to consent for the child should be provided*
- *Whether or not assent will be obtained from the child*
- *How will assent be documented*
- *Whether child subjects may be expected to attain legal age to consent to the procedures for research prior to the completion of their participation in the research. If so, describe the process that will be used to obtain their legal consent to continue participation in the study. Indicate what will occur if consent is not obtained from the now-adult subjects.*

--

*If the study involves cognitively impaired adults, additional information should be provided to describe:*

- *The process to determine whether an individual is capable of consent*
- *Indicate who will make this assessment*
- *The plan should indicate that documentation of the determination and assessment will be placed in the medical record, when applicable, in addition to the research record.*
- *If permission of a legally authorized representative will be obtained,*
  - *list the individuals from who permission will be obtained in order of priority*
  - *Describe the process for assent of subjects; indicate whether assent will be required of all, some or none of the subjects. If some, which subjects will be required to assent and which will not.*
  - *If assent will not be obtained from some or all subjects, provide an explanation as to why not*
  - *Describe whether assent will be documented and the process to document assent*
  - *Indicate if the subject could regain capacity and at what point you would obtain their consent for continued participation in the study*

--

*If the study will enroll non-English speaking subjects:*

- *Indicate what language(s) other than English are understood by prospective subjects or representatives*

- *Indicate whether or not consent forms will be translated into a language other than English*
- *Describe the process to ensure that the oral and written information provided to those subjects will be in that language*
- *If non-English speaking subjects will be excluded, provide a justification for doing so*

The study is committed to enrolling a racially and ethnically diverse population. We anticipate that most participants will have the competency to comprehend study materials produced in the English language at a 6th grade level, particularly when explained by trained clinical research coordinators. Exclusion of non-English speaking participants in this pilot study will not later negatively impact equitable access, participant comprehensibility or research design applicability to the diverse populations that may be solicited for participation in future clinical trials.

**24. WAIVER OR ALTERATION OF THE CONSENT PROCESS**     N/A

*Complete this section if you are seeking an alteration or complete waiver of the consent process.*

- *Describe the possible risks of harm to the subjects involved in this study and explain why the study involves no more than minimal risk to the subject:*
- *Explain why the waiver/ alteration will not adversely affect the rights and welfare of subjects*
- *Explain why it is impracticable to conduct this research if informed consent is required*
- *Explain why it is not possible to conduct this research without using the information or biospecimens in an identifiable form*
- *If appropriate, explain how the subjects will be provided with additional pertinent information after participation. If not appropriate to do so, explain why.*

Since the consent process will be remote and self-directed, it is not practicable or feasible for the investigator to sign the consent form in REDCap. As such, we request a waiver of the investigator’s signature for this research which is no greater than minimal risk. Individuals are encouraged to reach out to the study team via email and/or a direct phone line if they have any questions and prior to signing the consent form.

*Complete this section if you are obtaining informed consent but you are requesting a waiver of the documentation of consent (i.e., verbal consent will be obtained). To proceed with a waiver based on these criteria, each subject must be asked whether they wish to have documentation linking them to this study. **Only complete subsection 1 OR subsection 2.***

**SUBSECTION 1**

- *Explain how the only record linking the subject to the research would be the consent document.*

- Explain how the principal risk of this study would be the potential harm resulting from a breach in the confidentiality
- Indicate whether or not subjects will be provided with a written statement regarding the research.

**SUBSECTION 2**

- Describe the possible risks of harm to the subjects involved in this study and explain why the study involves no more than minimal risk.
- Confirm that the research only involves procedure for which consent is not normally required outside the research context.
- Indicate whether or not subjects will be provided with a written statement regarding the research.

**25. WAIVER OF HIPAA AUTHORIZATION**

N/A

**Complete this section if you seek to obtain a full waiver of HIPAA authorization to use and/or disclose protected health information.**

- Describe the risks to privacy involved in this study and explain why the study involves no more than minimal risk to privacy:
- Describe your plan to protect identifiers from improper use or disclosure and to destroy them at the earliest time.
- Indicate why it is not possible to seek subjects' authorization for use or disclosure of PHI.
- Indicate why it is not possible to conduct this research without use or disclosure of the PHI.
- Indicate if PHI will be disclosed outside NSLIJ Health System, and if so, to whom.  
Note: PHI disclosed outside NSLIJ Health System, without HIPAA authorization needs to be tracked. Please see guidance at [www.nslj.com/irb](http://www.nslj.com/irb) for information about tracking disclosures.

**Complete this section if you seek to obtain a partial waiver of the patient's authorization for screening/recruitment purposes (i.e., the researcher does not have access to patient records as s/he is not part of the covered entity)**

Note: Information collected through a partial waiver for recruitment cannot be shared or disclosed to any other person or entity.

- Describe how data will be collected and used:
- Indicate why you need the PHI (e.g. PHI is required to determine eligibility, identifiers are necessary to contact the individual to discuss participation, other)
- Indicate why the research cannot practicably be conducted without the partial waiver (e.g. no access to medical records or contact information of the targeted

*population, no treating clinician to assist in recruitment of the study population, other)*

--

## 26. VULNERABLE POPULATIONS:

Indicate whether you will include any of these vulnerable populations. If indicated, submit the appropriate appendix to the IRB for review:

- Children or viable neonate*
- Cognitively impaired*
- Pregnant Women, Fetuses or neonates of uncertain viability or nonviable*
- Prisoners*
- NSLIJ Employees, residents, fellows, etc*
- poor/uninsured*
- Students*
- Minorities*
- Elderly*
- Healthy Controls*

*If any of these populations are included in the study, describe additional safeguards that will be used to protect their rights and welfare.*

The Institute of Health System Science (IHSS) has established a good working relationship with Northwell Health Employees. From our past enrollment of NWH workforce, multiple individuals have expressed interest in participating in future IHSS trials, including pilots like this one. As such, Northwell Health Employees are ideal study subjects for this research.

All data, including this participant information, will be maintained by the study team on a Northwell-approved drive to store PHI. All members of the research team with access to identifiable and coded data will be trained and included on the IRB submission for approval.

The research will not interfere with NWH employees' job obligations. An employee's decision to participate or not participate will have no bearing on the employee's performance evaluation or employability at NWH. In addition, participants will be able to withdraw from the study at any time, for any reason without influencing their ability to receive health care and/or affect their employment status.

We do not intend to prevent study personnel or other employees of the Institute of Health System Science who express an interest in the research from participating. However, no supervisory personnel will be able to enroll participants who report to them in this research. We are not intentionally targeting minorities, but expect minorities to be part of those eligible for participation.

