## 5. RESOURCES AVAILABLE TO CONDUCT THE HUMAN RESEARCH

- *Explain the feasibility of meeting recruitment goals of this project and demonstrate a potential for recruiting the required number of suitable subjects within the agreed recruitment period*
  - *How many potential subjects do you have access to?*
- *Describe your process to ensure that all persons assisting with the trial are adequately informed about the protocol and their trial related duties and functions*

Northwell Health employs over 77,000 individuals. Inter-departmental support has been shown across Northwell to assist the researchers in meeting recruitment goals. Their extensive electronic communication system will allow for the rapid delivery of recruitment materials directly to potentially-eligible participants. Virtual electronic screening and consent processes, employment of participant smart phones for protocol reminders and notifications, and integration with existing Northwell Health policies will minimize burden to participate for those who are interested in the study.

Center for Personalized Health staff must meet certain eligibility criteria before assisting with this study. All staff members must be listed on the IRB and be up-to-date with trainings and attestations as required by the Northwell Health Human Research Protection Program. Additionally, staff will be required to participate in weekly meetings with the Principal Investigator and an additional weekly meeting with the Project Manager, in order to stay informed about the study protocol, staff duties and functions, and to answer any questions that come up within the group. Staff will have daily access to the Project Manager, Director of Clinical Research, and Principal Investigator to answer any protocol questions they may have outside these established weekly meetings.

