### **Exclusion Criteria**

- Age less than 18 years;
- Non-ambulatory or unsafe/not recommended to participate in a walking program;
- Not prescribed statin medication;
- History of CVD;
- Inability to comply with study protocol during 2 week run-in;
- Does not speak English;
- Unavailable for follow-up;
- Cognitive impairment;
- Severe mental illness (e.g., bipolar disorder or schizophrenia);
- Pregnancy

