*Environmental context and resources* is defined as aspects of a person’s situation or environment that discourage or encourage the behavior. This MoA will be assessed using a checklist of 7 potential barriers to physical activity identified by Steinhart and colleagues [29] Barriers are coded on a 1 (Not often at all) to 5 (Very often) scale, and averaged to create a total score, with higher scores indicating that the listed barriers had greater effects on walking.

Following completion of the 2-week run-in period, participants will receive a variable duration BCT intervention, and the length of the intervention is determined by utilization of the modified TiTE-CRM design. During the BCT intervention, participants will receive 5 daily BCTs via text message. Content of the text message will be specific for each BCT (e.g. a Goal Setting text message will encourage participants to develop a walking goal for the day). Initially, 3 participants will be treated at a moderate dose level, which is five weeks of the multi-BCT intervention to increase PA. Based on the calculated MED for the first cohort, subsequent cohorts will be administered a longer or shorter dose of the intervention. The BCT dose for each cohort will be determined by the study statistician based on the proportion of individuals in the prior cohort exhibiting the target behavior (in this case, a 2,000 step per day increase between baseline and follow-up periods). As the MED involves comparing PA levels between the run-in and follow-up periods, participants will not be assigned to subsequent cohorts unless all of the participants in the prior cohort have completed some of the intervention period. The treatment response for the prior cohort will be used to guide the dose administered to the subsequent cohort using modified TiTE-CRM methodology.

Following the completion of the intervention, all cohorts will be assessed for a 2 week follow-up period. Follow-up consists of wearing the activity monitor continuously, and use of electronic pill bottle to assess adherence. No interventions will be delivered during this period. At the end of the study, participants will be asked to complete the same questionnaire completed during baseline and the intervention phase as well as a satisfaction survey regarding the BCT intervention. Participants will also be reminded/instructed to return their eCAP smart pill bottle to the study team via addressed packaging included in their study materials.

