## 12. STATISTICAL ANALYSIS

- *Describe how your data will be used to test the hypotheses.*
- *State clearly what variables will be tested and what statistical tests will be used.*
- *Include sample size calculations.*
- *If this is a pilot study, state which variables will be examined for hypothesis generation in later studies.*

Analysis for the Primary Aim: The minimum effective dose (MED) will be defined as the smallest BCT dose duration associated with a successful PA increase (defined as an average increase of 2,000 steps per day) between the 2-week run-in and 2-week follow-up periods in at least 80% of participants. The MED will be estimated based on the modified TiTE-CRM, which is an adaptive model-based, dose-finding design for estimating the maximum tolerated dose in pharmacologic agents. In this study, we will adapt the TiTE-CRM for the purpose of MED estimation. Briefly, the TiTE-CRM operates as follows during a study. Participants will be enrolled in cohorts of 3. The first cohort will be given a BCT intervention with a duration of 5 weeks. Subsequent cohorts will be given a BCT intervention duration (from 1-week to 10-week) based on the updated MED estimate according to the modified TiTE-CRM model and data from the previously enrolled participants. The process will continue until we reach a total of 42 participants (14 cohorts) randomized to the intervention. Once the study has completed enrollment, we will identify which dose of the BCT intervention (in weeks) is associated with  $\geq 80\%$  of participants achieving the goal of an average of 2,000 steps per day increase between the baseline and follow-up periods. Means and standard deviations of step scores for baseline versus behavioral change strategy treatment period will be visualized using a column graph. The statistical significance of differences will be adjusted for time interval. The effects of treatment on number of steps will be assessed using generalized linear mixed models (GLMM). This model will account for possible autocorrelation and linear trends between steps across time.

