#### Eligibility, Consent, and Survey and Fitbit Data

Survey and Fitbit data will be collected and stored using RedCap, which is a Northwell security-review approved system for collecting and storing research data, including PHI. The study team will have access to all data, including PHI, throughout the study. Pooled results will be used to assess gaps in phenotypic understanding to empirically determine if modeling precise therapy is feasible.

The study team takes data confidentiality very seriously. Data collected for this research will be maintained on a HIPAA-compliant Northwell-approved SQL database. All members of the research team with access to identifiable and coded data will be trained and included on the IRB submission for approval. Regular meetings will take place with the PI and other members of the study team to ensure protocol adherence and data accuracy. Data collected for this study will be maintained in its original and unaltered source data state in a Northwell-approved SQL database on a Northwell-approved drive to store PHI indefinitely. Data collected under this research may be used for future research in coded format without additional consent as per the consent form participants sign and with appropriate IRB approval as required. Any additional data that must be shared will be done so

according to the consent form participants signed. Only research staff listed within this IRB submission will have access to identifiable information. Anonymized data may be stored indefinitely for reference following the conclusion of the study. The participant will be made aware of all data collected in the consenting process.

This research is funded by the NIH, thus a Certificate of Confidentiality has been issued for this research. Certificates of Confidentiality (CoCs) protect the privacy of research subjects by prohibiting disclosure of identifiable, sensitive research information to anyone not connected to the research except when the subject consents or in a few other specific situations.

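### Study personnel may enrol in a trial whose primary outcome is their own change in walking; the bias would favour too short a duration, is probably small, and costs one exclusion line to remove

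*Combined protocol and SAP*

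**What the plan says.** Section 26 (Vulnerable Populations) states "We do not intend to prevent study personnel or other employees of the Institute of Health System Science" from taking part if they wish to. It sets one limit: "However, no supervisory personnel will be able to enroll participants who report to them in this research". That protects against pressure on employees; it does not bear on who contributes outcome data.

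None of the ten exclusions in section 7 concerns study staff. The nearest is "Inability to comply with study protocol during 2 week run-in", which is about compliance.

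Four other statements matter here:

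- Section 12 defines the outcome as a "successful PA increase (defined as an average increase of 2,000 steps per day) between the 2-week run-in and 2-week follow-up periods".
- Section 5 has staff attend weekly meetings "in order to stay informed about the study protocol, staff duties and functions, and to answer any questions that come up within the group".
- Section 14 says "The study team will have access to all data, including PHI, throughout the study".
- Section 11 says "The BCT dose for each cohort will be determined by the study statistician based on the proportion of individuals in the prior cohort" reaching the step target.

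The plan describes no blinding, no separation of staff participants from the accumulating data, and no analysis that sets staff participants aside.

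**The concern.** The outcome is device-measured, so false reporting is not the issue. The Fitbit does, however, record behaviour that the participant controls. Someone who works on the study knows the threshold and which two 2-week windows are compared, and may see how cohorts are doing. Such a person may, without intending it, walk less in run-in and more in follow-up. Walking less in run-in also helps to meet the Fitbit-verified low-activity criterion in section 7, which has no numeric cut-off.

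If staff succeed more or less regardless of the assigned duration, short durations look better than they are and the MED estimate moves down. The trial would then tend to carry forward a duration that falls below the 80% target in people outside the study team.

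**Working it through.** **Inputs from the documents.** 42 participants in 14 cohorts of 3; first cohort at 5 weeks; durations from 1 to 10 weeks; target success 80%; calibration to within 5 percentage points of target; logistic curve with slope 0.69 (odds ratio 2); stated probability of correct selection (PCS) 60% (sections 8, 9 and 12).

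**Assumptions not in the documents.** Ten weekly levels; slope 0.69 per level; one-parameter power-model CRM on the failure scale (target failure 0.20); prior MED at level 5; normal prior with mean 0 and variance 1.34; complete follow-up, so no time-to-event weights; no limit on skipping levels; true success exactly 80% at the MED.

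**Step 1: reproduce the plan's figure.** At 80% the odds are 4. At an odds ratio of 2 per level, the level below has odds 2 (success 66.7%) and the level above odds 8 (88.9%). Only the MED itself then lies within 5 points of target, so correct selection means selecting exactly the MED. With 2,000 runs per true MED and half-width 0.05, mean PCS is 0.603 for MEDs at levels 2 to 9 and 0.633 for all ten. With half-width 0.07 these are 0.619 and 0.626; with 0.10, 0.576 and 0.546. The stated 60% is reproduced.

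**Step 2: add staff, worst case.** Let m of the 42 be staff who always succeed, placed at random in the enrolment order. Results average over true MEDs at levels 2 to 9, with 4,000 runs each (half-width 0.05).

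| Staff m | Correct | Too short | Too long | Mean error (levels) |
|---|---|---|---|---|
| 0 | 60.8% | 14.3% | 25.0% | +0.117 |
| 1 | 60.4% | 16.4% | 23.2% | +0.076 |
| 2 | 60.6% | 18.6% | 20.8% | +0.028 |
| 3 | 60.1% | 21.2% | 18.7% | -0.021 |
| 4 | 59.6% | 23.7% | 16.7% | -0.069 |
| 6 | 57.1% | 30.1% | 12.8% | -0.179 |

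Each row rests on 8 × 4,000 = 32,000 runs, so the Monte Carlo standard error of the 14.3% is √(0.143 × 0.857 / 32,000) ≈ 0.2 points.

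**Step 3: check by hand.** If staff are spread evenly over durations, 80% overall success is reached when non-staff success is (0.8 × 42 − m)/(42 − m), that is, odds of (33.6 − m)/8.4. The implied shift in levels is [ln 4 − ln((33.6 − m)/8.4)]/0.69.

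- m = 1: non-staff success 32.6/41 = 79.5%; odds 3.881; shift (1.386 − 1.356)/0.69 = 0.04. Simulated: 0.117 − 0.076 = 0.041.
- m = 3: 30.6/39 = 78.5%; odds 3.643; shift (1.386 − 1.293)/0.69 = 0.14. Simulated: 0.117 + 0.021 = 0.138.
- m = 6: 27.6/36 = 76.7%; odds 3.286; shift (1.386 − 1.190)/0.69 = 0.29. Simulated: 0.117 + 0.179 = 0.296.

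The two agree. The effect is a small downward shift: too-short errors replace too-long ones while the total error rate hardly moves. PCS alone would therefore not reveal it.

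**The case against.** **Much of the mechanism is not specific to staff.** All participants control their own walking, set goals, monitor themselves and get feedback (section 11), and all receive a written account of purpose and procedures (section 23). The consent pages are not in the reviewed text, so it cannot be said that only staff know the 2,000-step figure. Seeing other people's data is not needed to change one's own walking, and the statistician sets the dose. This stands in part: what distinguishes staff is the weekly briefing and the access to accumulating data.

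**Few staff can qualify.** They must take a statin, have no history of CVD, and report and show low activity. They must also hold 2,000 extra steps a day through two weeks without messages, so certain success is an upper bound. This stands and limits the weight of the point.

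**Two stronger readings are not supported.**

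- A reader might infer that a few staff at one duration would lift an inadequate duration into the 75%-85% range of section 12. For example, with true success 70% and 3 staff among 12, expected observed success is (0.70 × 9 + 3)/12 = 77.5%. But that range calibrates the success rate at the duration the model selects; it is not an acceptance rule for an observed proportion. Neither 12 per duration nor 3 staff among them is in the documents. With 3 staff spread over all 42, the expected number per 12 is 0.86 and the figure is (0.70 × 11.14 + 0.86)/12 = 72.1%.
- A reader might infer that one staff member swings a third of the evidence, because cohorts have 3 members. Section 11 does speak of the prior cohort, but sections 9 and 12 base each assignment on data from previously enrolled participants, so one person's weight falls as the trial proceeds. Putting three staff in the first cohort gives 19.3% too-short selection, not more than the 21.2% with random placement.

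**Conclusion.** The concern holds as a minor point. The plan expressly allows study personnel into a trial whose outcome they control and whose threshold they know, and no other section cures this. Any bias would run toward too short a duration.

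Its size is uncertain. Under the worst case, one staff member adds about 2 points to the chance of selecting too short a duration, three add about 7, and six about 16, while PCS goes from 61% to between 60% and 57%. The assumptions are certain staff success, the CRM form and prior, ten weekly levels, the slope per level and complete follow-up; none is stated in the documents except the slope value itself. Confidence is high on the text and low on the magnitude.

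The documents do not show that staff have enrolled or would alter their walking, and they do not support a claim that the stated 60% is undermined. That no participant is blinded is inferred from the absence of any description of blinding.

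**What to change.** Add an exclusion to section 7 for anyone listed on the IRB application for this protocol as study personnel, and for anyone with access to its outcome data or dose assignments. Amend the section 26 sentence to match. Other institute employees, with no role in this study and no such access, stay eligible, and the bar on supervisors enrolling their own reports stays.

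If any staff are already enrolled, record staff status and re-estimate the MED without them as a sensitivity analysis, reported beside the main estimate.

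The cost is a short amendment and a handful of potential participants. The study needs 42 from a workforce of over 77,000 (section 5) plus patients identified through prescription records (section 6).
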